Our hypothesis is that introducing a benign probiotic (beneficial intestinal bacteria) using Align probiotics will cause improvement in hepatocellular (liver tissue) injury and fibrosis. Align is a once daily over-the-counter defined by the Food and Drug Administration as a new dietary ingredient. Each Align capsule contains one billion beneficial live bacteria/CFU, known as Bifidobacterium 35624. Our goal is to provide data that probiotics may be a viable treatment option in the future for clinicians for NAFLD and NASH and to establish a link that the intestinal microbiome plays a role in liver inflammation.

IRB NUMBER: 2019-129
IRB APPROVAL DATE: 04/07/2021

Primary Endpoint:

To determine if probiotic use improves fibrosis stage on transient elastography

Secondary Endpoints:

To determine if probiotic use improves:

- 1) Liver Enzymes (AST and ALT)
- 2) Hemoglobin A1C (Diabetic Marker)
- 3) BMI (Body Mass Index)
- 4) Lipids (LDL)

METHODS

NAFLD and NASH patients seen in office consultation at South Oakland Gastroenterology Associates in Farmington Hills, Michigan from 2019-2021 who have confirmed diagnosis of NAFLD or NASH and fit the eligibility requirements will be approached to participate in the double-blind, placebocontrolled study.

After preparation and randomization by the Beaumont research pharmacy, the probiotic and placebo capsules will be delivered to the office in groups of 10 bottles at a time. Capsule bottles will be numbered consecutively and pharmacy will keep the randomization log; patients and researchers will be blinded. The bottles will be stored in a locked cabinet in the clinic. Only pharmacy will hold the randomization key. A log will be used to track the receipt and distribution of the capsules.

After informed consent is obtained, subjects will be counseled on diet and exercise and a baseline transient elastography exam will be ordered and baseline liver enzymes (AST and ALT) will be drawn, including hemoglobin A1C, lipids in the form of LDL and assessment of BMI (all standard of care tests). The patients will receive information on a standardized Mediterranean diet based nutrition program as well as direction for recommended 30 minutes of aerobic exercise 3 times weekly. Our recommended nutrition program limits excessive alcohol to avoid a confounding variable.

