Patients will be randomized by pharmacy into 2 groups, a control group and a treatment group. The treatment group will be provided with a 6 month supply of probiotic supplementation; the control group will be given a placebo for 6 months along with instructions on how to take the supplement. Subjects will receive a 1 month (+/- 1 week) phone call follow up to ensure adherence to study instructions and daily oral intake of supplement and again at 3 months (+/- 1 week).

Study participation will end at 6 months (+/- 2 weeks) after the repeat of liver enzymes, hemoglobin A1C, lipid panel, assessment of BMI and transient elastography as completed at scheduled clinical appointment.

TABLE OF EVENTS

	Pretreatment	1 month +/-1 week	3 month +/-1 week	6 month +/-2 weeks
Consent	Х			
Capsules dispensed	Х			
Diet & exercise plan explained	Х	Х	Х	
Labs drawn	Х			Х
Liver scan done	Х			Х
Phone call		Х	Х	
Remaining capsules returned				Х

RISKS AND BENEFITS

The FDA has identified the study as minimal risk and exempt of the need for an IND number.

There are currently no alternative treatments or procedures indicated in this disease process, hence, the purpose of the study. However, potential benefits to subjects from exercise (walking) intervention and nutritional coaching may improve the elasticity and function of the liver.

Potential risks include GI symptoms related to probiotic use such as gas and bloating. The recommended exercise is walking.

VI. ELIGIBILITY CRITERIA

Inclusion Criteria:

- Diagnosis of NAFLD and/or NASH
- Subject aged 18 and older
- Non-pregnant Self-reported
- Subject with decision making capacity to understand and consent to study procedures
- Ability to follow study related activities regarding medications, diet and exercise

Exclusion Criteria:

• Without diagnosis of NAFLD or NASH

- History of liver disease from other causes, including but not limited to hepatitis, autoimmune, alcohol use, fatty liver of pregnancy, Wilson's disease, primary or secondary hemochromatosis
- Patients aged less than 18 years
- Self-reported pregnant patients
- Inability to understand, follow and consent to study procedures
- Received a liver scan greater than 2 months prior to enrollment
- Patient lost more than 5 pounds of weight in the last 2 months
- Hepatic decompensation defined as gastrointestinal bleeding, ascites, hepatic encephalopathy
- Inability to engage in exercise
- Currently immunocompromised or taking immunosuppressive drugs

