- Milk protein allergy
- Recent or active chemotherapy for malignancy
- Gastrointestinal malignancy
- Gastrointestinal disease such as Ulcerative Colitis, Crohn's Disease as these alter the microbiome
- Recent antibiotic therapy (within 6 months)
- Known allergy to probiotics
- History of major gastrointestinal surgery such as resection of the colon
- No concomitant use of probiotic from any source (i.e., kefir, certain yogurts, live culture sauerkraut)
- Any implanted battery operated device (i.e. AICD, pacemaker, loop recorder, cochlear implant)

DATA COLLECTION

Any changes to the liver will be documented using a non-invasive scan called transient elastography. Elastography is a technique similar to ultrasound that measures the stiffness and density of the liver and is a safer alternative to a liver biopsy. This is a standard of care procedure will be done at 0 months and 6 months. Along with the scans, the results of liver enzymes, standard of care laboratory tests used to follow the disease progression for patients with NAFLD and NASH, will be reviewed. These labs include AST and ALT, Hemoglobin A1C, BMI (Body Mass Index) and Lipids (LDL), also standard of care.

DATA ANALYSIS

A. Sample Size Consideration

Using paired measurements, a two-tail alpha of 0.05, a power level of 0.8, and assuming a large effect size (contingency coefficient of 0.447), it is estimated that 40 subjects (20 per group) would detect statistically significant between-group changes in liver function. Related studies on hepatic function (Wong, et al., 2013 and Aller, et al. 2011) following administration of probiotics over 6 and 3 months 03.30.2021

IRB APPROVAL DATE: 04/07/2021

duration demonstrated statistically significant changes with estimated large effect sizes using 20 and 28 subjects, respectively. A sample size of approximately 40 is expected to hold statistical significance, however, to account for dropouts or potential removal of subjects from study, a goal of 80 subjects are expected to be enrolled to ensure adequate sample size.

B. Statistical Methodology

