Categorical data will be summarized as counts and percentages, and continuous data as means with corresponding standard deviations. Pre- post- results will use the chi-square test for association for nonparametric data or analysis of covariance for parametric data. Because multiple measures will be obtained for achieving the secondary objectives, multivariate analyses will be used for exploring overall treatment effects. Throughout this study, a p-value<0.05 (two-tail) will be considered statistically significant.

DATA AND SAFETY MONITORING PLAN

The Principal Investigator and the co-investigators will do safety monitoring. Ongoing assessment of subject safety will be monitored during subject phone calls as detailed in methodology. Any reported problems will be discussed with Medical Monitor/ Principle Investigator. Subjects with any signs or symptoms of hepatic decompensation or elevated liver enzymes beyond three times the upper limit of normal will be removed from the study, the study will be aborted for that subject and immediate diagnostic and/or therapeutic modalities will be delivered. It should be noted that our study is defined as minimal risk as also identified by the FDA with the exemption of need for an IND number.

Any subject found to be noncompliant with the protocol will be removed from the study and asked to return their medications to the office. The medications will then be returned to the research pharmacist.

All data will be kept electronically in a secure SharePoint site. Hard copies will be kept in a locked file located in a locked office until the study ends. Hard copies will then be scanned into the SharePoint site and shredded per Beaumont policy.

REFERENCES

[1] The Liver Meeting, Post-Graduate Seminar, New Research, American Association for the Study of Liver Diseases, Washington, D.C., 2017

Velasco, Nicolas; Contreras, Alvaro; Grassi, Bruno. The Mediterranean diet, hepatic steatosis and nonalcoholic fatty liver disease. Current Opinion in Clinical Nutrition & Metabolic Care. 17(5):453-457, September 2014.

Attachments

- A. PRONE Study Informed Consent Form and Authorization for Disclosure of Protected Health Information
- B. PRONE Study FDA 2018-1186 Signed Final Response
- C. PRONE Study Nutrition Program

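### Fibrosis stage, the primary endpoint, has no assigned test; the one named test that fits it either does not compare the arms or ignores stage order and baseline stage

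*Combined protocol and SAP*

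**What the plan says.** - Objectives, Primary Endpoint: "To determine if probiotic use improves fibrosis stage on transient elastography". The stages are not listed, and improvement is not defined.
- Data Collection: the scan "measures the stiffness and density of the liver", and on timing, "This is a standard of care procedure will be done at 0 months and 6 months". Each patient who completes therefore has a baseline and a 6-month stage.
- Data Analysis, B. Statistical Methodology: "Pre- post- results will use the chi-square test for association for nonparametric data or analysis of covariance for parametric data". Neither test is tied to an endpoint. The multivariate analyses mentioned next are for the secondary objectives only.
- Data Analysis, A. Sample Size Consideration: "Using paired measurements, a two-tail alpha of 0.05, a power level of 0.8", "assuming a large effect size (contingency coefficient of 0.447"), leading to 40 subjects, 20 per group, to detect a difference in change between the groups.
- Methods: after consent, "subjects will be counseled on diet and exercise and a baseline transient elastography exam will be ordered". This applies to both arms. Risks and Benefits adds that "potential benefits to subjects from exercise (walking) intervention and nutritional coaching may improve the elasticity and function of the liver".

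**The concern.** A stage is not parametric data in the plan's sense, so the chi-square is what remains for the primary endpoint. ANCOVA would suit continuous stiffness, but stiffness is not the stated endpoint. The layout of the chi-square table is left open, and two readings are possible.

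**Reading A, before against after.** The methods sentence refers to results before and after, and the sample size section opens with paired data. A time-by-stage table does not compare the randomised arms, and it treats two measurements on one patient as independent. Both arms receive diet and exercise advice that the protocol itself expects may help the liver. A shared improvement could therefore give a significant primary result with no probiotic effect.

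**Reading B, by arm.** The comparison is valid. However, a chi-square of association treats the stages as unordered and does not adjust for baseline stage. An improved/same/worse table uses baseline only to form the category. What is at stake here is power, not the error rate.

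**Working it through.** **1. Reproducing the plan's 40.** Convert the contingency coefficient to Cohen's w:

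w = C/√(1 − C²) = 0.447/√(1 − 0.1998) = 0.447/0.8945 = 0.4997

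Power comes from the noncentral chi-square with noncentrality N·w². At N = 40 this is 40 × 0.2497 = 9.99.

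| df | N for 80% power | Power at N = 40 |
|---|---|---|
| 1 | 32 | 0.885 |
| 2 | 39 | 0.815 |
| 3 | 44 | 0.761 |
| 4 | 48 | 0.715 |

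The stated 40 matches df = 2, for example two arms by improved/same/worse. It also matches df = 1 if 0.447 is itself taken as w (N = 40). Neither calculation uses pairing. The 40 was therefore already sized for a chi-square of association, and the losses in step 4 are not a charge on the margin between 40 and 80.

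**2. Simulation assumptions.** The documents give no number of stages, stage distribution, baseline to 6-month correlation (r) or shift, so these are assumed. A bivariate normal latent measure is cut into 5 stages with shares 30/25/20/15/10, 20 each, or 50/20/15/10/5 percent; r is 0.6, 0.7 or 0.8; 20,000 trials per setting. The comparator, rank ANCOVA, is a linear model of ranked 6-month stage on arm and ranked baseline stage.

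**3. Reading A: no probiotic effect, both arms improve equally.** Share of trials in which the pooled time-by-stage chi-square has p < 0.05:

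| Common improvement | N = 40 | N = 80 |
|---|---|---|
| 0.3 SD | 0.035-0.073 | 0.088-0.171 |
| 0.5 SD | 0.154-0.271 | 0.502-0.674 |
| 0.8 SD | 0.585-0.822 | 0.964-0.999 |

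On the same data the between-arm rank ANCOVA rejects in 0.047-0.054 and the arm-by-change chi-square in 0.033-0.054. Reading A also misses real effects. With a true 0.8 SD effect in the probiotic arm only (r = 0.7, 2,500 trials), the pooled table is significant in 8-12% of trials at N = 40, against 68-83% for rank ANCOVA.

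**4. Reading B: arm by improved/same/worse against rank ANCOVA.** With no effect and no change, both reject in 0.048-0.053. Relative loss = 1 − power(chi-square)/power(rank ANCOVA). For the first distribution with r = 0.7:

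| Shift | Per arm | Chi-square | Rank ANCOVA | Loss |
|---|---|---|---|---|
| 0.5 SD (w = 0.24) | 20 | 0.250 | 0.432 | 1 − 0.250/0.432 = 42% |
| 0.8 SD (w = 0.35) | 20 | 0.495 | 0.793 | 1 − 0.495/0.793 = 38% |
| 0.5 SD | 40 | 0.478 | 0.731 | 1 − 0.478/0.731 = 35% |
| 0.8 SD | 40 | 0.843 | 0.980 | 1 − 0.843/0.980 = 14% |

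- All 5-stage settings at 0.5-0.8 SD (w = 0.20-0.42): loss 25-47% at 20 per arm and 4-41% at 40 per arm.
- 3 to 5 stages, r 0.5-0.9 (w = 0.18-0.50; 8,000 trials): 12.6-50.5% and 0.3-46.5%.
- At the plan's own w = 0.50, reached in 4 of the 9 five-stage settings at shifts of 1.12-1.75 SD: 0.873-0.891 against 0.994-1.000 at 20 per arm, a loss of 10.8-12.2%. At 40 per arm the loss is 0.1-0.3%.
- The simulated 0.873-0.891 is above the 0.815 from the noncentral chi-square, which is a large-sample approximation. Taking 0.815 instead, the loss cannot exceed 1 − 0.815/1 = 18.5%.

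**5. Where the power goes if the table is 6-month stage by arm.** With 5 stages, either equal or 35/25/20/12/8 percent, r 0.5-0.85, a 0.8 SD shift and 20 per arm (2,000 trials), the chi-square has power 0.32-0.40. A rank-sum test, which uses order, has 0.57-0.65. Rank ANCOVA, which also uses baseline, has 0.66-0.94.

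**The case against.** The by-arm reading is the more natural one. The same sentence covers ANCOVA, which is normally a comparison of groups. The trial is randomised against placebo, the sample size section speaks of change between groups, and its 40 fits a two-by-three table. The most serious harm therefore sits on the less supported reading, and its size depends on a common improvement that the protocol does not quantify. At 0.3 SD and 40 patients the rejection rate is about nominal.

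Under the by-arm reading the test is valid. At the effect the plan assumes, it already exceeds 80% power at 20 per arm, and the loss at 40 per arm is negligible. Preferring another valid test is partly a matter of choice, and a one-line clarification of the table would remove the before-against-after reading. It can also be said that the plan does assign tests, by type of data.

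Much of this stands: by arm is the better-supported reading, every size depends on assumptions, and the loss is small at the plan's own effect. It does not remove the point. Nothing in the plan fixes the table, the stages or the link to the primary endpoint, so the primary test could be chosen after the data are seen. Clarifying the table alone would still leave order and baseline stage unused, although both are already collected.

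**Conclusion.** The concern holds and should be fixed. That the primary endpoint has no specified analysis is certain from the text. If the chi-square is run before against after, its p-value does not answer the primary question; how often it misleads depends on how much both arms improve. If it is run by arm, the error rate is correct and the issue is efficiency: modest at the plan's own large effect, and larger if the true effect is smaller. The direction of the loss was the same in every setting tried. Its size depends on the assumed stages, correlation and shift, and on there being no common improvement. Adding a 0.3 SD improvement to both arms raised the 20-per-arm loss at 0.5-0.8 SD to 49-73% (5 stages, 12,000 trials), which is a sensitivity result only.

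**What to change.** Replace the sentence on before and after results in Data Analysis, B. Statistical Methodology with:

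> The primary analysis compares the randomised groups on 6-month fibrosis stage, in the stage categories defined in this plan, by rank analysis of covariance with arm and baseline stage as terms, two-sided 0.05. A proportional-odds odds ratio with 95% CI, using the same terms, is a supportive estimate only; if it disagrees with the rank test, the rank test decides. AST, ALT, HbA1c, BMI and LDL are compared between arms by ANCOVA with the baseline value as covariate. Within-arm changes from baseline are descriptive only.

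The order of precedence needs stating. In simulation (first distribution, r = 0.7, 20 per arm, 3,000 trials) the odds-ratio interval and the rank test disagreed in 1.9% of trials with no effect, 8.5% at 0.5 SD and 6.5% at 0.8 SD. Among trials with a rank p-value between 0.02 and 0.10 they disagreed in 22-29%.

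Also define the stage categories, and say how the secondary ANCOVAs relate to the exploratory multivariate analyses already planned. Restate the sample-size basis for the rank test, giving the assumed stage distribution, the baseline to 6-month correlation and the difference to be detected.

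The cost is SAP wording and a revised sample-size paragraph. No visits or measurements are added, because stage is already obtained at 0 and 6 months.

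### Could the undefined parametric/nonparametric rule send AST and ALT to a chi-square test and lose power?

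*Combined protocol and SAP*

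**What the plan says.** The only rule for choosing a test is in DATA ANALYSIS, section B: pre-post results go to a "chi-square test for association for nonparametric data or analysis of covariance for parametric data". Neither term is defined, and no distributional check, transformation or rank method is mentioned. The sentence before it reads "Categorical data will be summarized as counts and percentages, and continuous data as means with corresponding standard deviations". For the secondary objectives as a group, "multivariate analyses will be used for exploring overall treatment effects", with no method named.

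The primary endpoint under OBJECTIVES is "To determine if probiotic use improves fibrosis stage on transient elastography". The secondary endpoints are AST and ALT, HbA1c, BMI and LDL. DATA COLLECTION lists them as measured values: "These labs include AST and ALT, Hemoglobin A1C, BMI (Body Mass Index) and Lipids (LDL), also standard of care". No analysis cut-off is given for any of them. The table of events has labs before treatment and at 6 months only.

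Section A (Sample Size Consideration) arrives at 40 subjects, 20 per group, "assuming a large effect size (contingency coefficient of 0.447", and says that this number "would detect statistically significant between-group changes in liver function". The enrolment goal is 80.

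**The concern.** Parametric and nonparametric normally describe methods or distributional assumptions, not types of data. Liver enzymes are often handled as skewed, so a literal reader could call them nonparametric and send them to chi-square. They would then have to be cut into categories that the plan does not define, and the baseline value would no longer serve as a covariate.

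Section A seems to support that reading. It sizes changes in liver function with a contingency coefficient, which is an effect measure for tables of counts.

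Two things would be at stake: power on the secondary enzyme endpoints and, if the test were picked after seeing results, the false-positive rate.

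**Working it through.** **1. The plan's own sample size.** Inputs from section A: contingency coefficient C = 0.447, two-sided alpha 0.05, power 0.80, N = 40.

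- Conversion: w = C/√(1 − C²) = 0.447/√(1 − 0.1998) = 0.4997. The noncentrality is N·w².
- N needed for 80% power: 32 with 1 degree of freedom, 39 with 2, 44 with 3, 48 with 4.
- With 2 degrees of freedom at N = 40, the noncentrality is 40 × 0.2497 = 9.99 and power is 81.5%.
- If 0.447 is used directly as w with 1 degree of freedom, the noncentrality is 40 × 0.1998 = 7.99, power is 80.7% and the required N is exactly 40.

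The figure of 40 therefore reproduces as a two-arm table with three outcome categories, or as a 2×2 table without the conversion. Either is a calculation for a categorical outcome. The categorical endpoint in this plan is fibrosis stage, which is also the primary, and a trial is normally sized on its primary. The coefficient is thus weak evidence that enzymes were meant for chi-square.

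**2. The two readings side by side.**

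| | Categorical v continuous | Literal (distributional) |
|---|---|---|
| Support in the text | Preceding sentence in section B; enzymes listed as values without cut-offs | The words themselves; the contingency coefficient in section A |
| Test for AST and ALT | ANCOVA | Chi-square if skewed |
| What must be invented | Nothing essential: one baseline and one 6-month value give one obvious ANCOVA | A skewness criterion and the categories |

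**3. Size if the literal reading were followed.** All inputs are assumptions, not in the documents: log-normal ALT, median 50 or 60 U/L, log-SD 0.5 or 0.6, pre-post correlation 0.5 or 0.7, a 25% proportional reduction, upper limit of normal (ULN) 40 U/L. These give 8 parameter cells, with 10,000 simulated trials each.

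| Test | Power, 20 per arm | Power, 40 per arm |
|---|---|---|
| Chi-square, above ULN yes/no | 20–28% | 36–54% |
| Chi-square, decreased yes/no | 21–43% | 40–73% |
| ANCOVA, raw scale | 33–61% | 59–90% |
| ANCOVA, log scale | 39–69% | 68–94% |

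Compared cell by cell, raw ANCOVA exceeds chi-square by 11 to 42 points (12 to 42 for the ULN split, 11 to 24 for any decrease). The safety section says subjects with "elevated liver enzymes beyond three times the upper limit of normal will be removed from the study"; dropping subjects above 3 × 40 = 120 U/L at either visit gives 8 to 39 points.

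**4. Size on the natural reading.** Only the scale of the ANCOVA is open. Log exceeds raw by 5 to 10 points (2 to 6 with removal).

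**5. Sensitivity to the assumed form.**

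- Constant shift of 25% of the median on the same log-normal data: raw ANCOVA runs from 6 points below chi-square to 20 above (5 to 32 above with removal), and log exceeds raw by 18 to 38 (11 to 24 with removal).
- Normal values with SD 40 to 48% of the median: log falls 4 to 9 points below raw.

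**6. Error rate.** Under no effect, each single test rejected in 3.8 to 6.0% of runs.

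**The case for a change.** The strongest case for a change is that the plan does not fix the test in advance, so the 5% error of each single test is little comfort. If an analyst could report the best of the ULN split, any decrease and raw ANCOVA, null simulations reject in 11 to 13% for one enzyme. One added sentence would close that route at no cost in data or visits. The plan also uses its categorical/continuous wording only for summaries, then switches terms for testing.

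Part of this stands. The terms are misused, no individual endpoint is paired with a test, and the unnamed multivariate analyses do not settle the matter. But 11 to 13% is an upper bound for unrestricted choice after seeing the results. In null runs at one central parameter set, choosing the test by a normality check stayed near 5%. Researchers are blinded and only the pharmacy holds the randomisation key. To reach the upper bound, an analyst would have to invent cut-offs for laboratory values and pass over the ANCOVA that the plan already names. The secondary multivariate work is also described as exploring effects, so little confirmatory weight rests on the enzymes.

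**Conclusion.** No change follows on this point. Read with the sentence before it, the rule means chi-square for categorical variables and ANCOVA for continuous ones. AST and ALT then already get baseline-adjusted ANCOVA. Spelling that out would record what an analyst would do anyway.

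The loss of 11 to 42 points belongs to the less natural reading. It rests on a distribution, an effect size and a ULN that the documents do not give, and under a constant shift the comparison can even reverse by up to 6 points. A mandatory log scale is not a clear gain: plus 5 to 10 points if the enzymes are log-normal with a proportional effect, minus 4 to 9 if they are symmetric. That choice can reasonably be made on blinded data. There is no validity fault in any single test, at about 4 to 6% error.

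This conclusion covers the enzymes only. The plan does not spell out the test and categories for fibrosis stage, where an unnamed test matters most. That is a separate question, and the enzyme figures neither support nor dismiss it.

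### Five secondary markers share an unadjusted two-sided 0.05 rule, and the planned multivariate analysis is not tied to claims about single markers

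*Combined protocol and SAP*

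**What the plan says.** All references are to the combined protocol and SAP.

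- **Objectives, Secondary Endpoints.** The list opens with "To determine if probiotic use improves" and has four numbered items. The first item holds both AST and ALT, so there are five measures: AST, ALT, HbA1c, BMI and LDL. The primary endpoint, fibrosis stage on transient elastography, is introduced by the same phrase.
- **Data Analysis, B. Statistical Methodology, test for each measure.** "Pre- post- results will use the chi-square test for association for nonparametric data or analysis of covariance for parametric data".
- **Same section, several secondary measures.** "Because multiple measures will be obtained for achieving the secondary objectives, multivariate analyses will be used for exploring overall treatment effects".
- **Same section, significance rule.** "Throughout this study, a p-value<0.05 (two-tail) will be considered statistically significant".

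Nowhere does the document set a multiplicity adjustment, an order of testing, a restriction of the significance rule to the primary endpoint, or an exploratory label for the secondary endpoints. The multivariate method is not named.

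**The concern.** The significance rule reaches every test, and the secondary questions are put in the same terms as the primary one. Read literally, one marker of five with p below 0.05 may be reported as a statistically significant improvement, even if the fibrosis comparison shows nothing.

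The hypothesis in the Objectives covers both liver-cell injury and fibrosis. Of the listed endpoints, the two enzymes are the ones that plausibly speak to injury. A lone AST or ALT result could therefore easily be presented as support for the hypothesis, in a trial meant to supply data on probiotics as a possible future treatment.

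The multivariate sentence shows that the authors saw the issue, but it does not settle it. An overall test asks whether anything differs across the set. By itself it does not say which marker moved or whether the movement was a benefit, and the Objectives ask exactly that. The plan has no rule that links the overall result to a claim about one marker.

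**Working it through.** **Inputs from the document.** Five secondary measures (Objectives); two-sided 0.05 for each test, with no adjustment (Statistical Methodology).

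**Inputs assumed.** Each marker is tested and claimed separately. None truly changes. The document gives no correlations among the markers, so a common correlation is varied from 0 to 0.9.

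The plan states no error rate for the set of secondary tests, so there is no figure of its own to reproduce. Its sample-size figure does not bear on this point.

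**Step 1. Any false significant result, either direction.**
- Independent tests: 1 − 0.95^5 = 0.226.
- Bound under any dependence: 5 × 0.05 = 0.25.

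**Step 2. A false benefit.** A two-sided 0.05 test puts 0.025 in the favourable tail.
- Independent tests: 1 − 0.975^5 = 0.119.
- Bound: 5 × 0.025 = 0.125.

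**Step 3. Correlated markers.** Simulated with 1,000,000 draws of five normal test statistics with equal correlation, critical value 1.96:

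| Assumed correlation | Any false result | False benefit |
|---|---|---|
| 0 (formula) | 22.6% | 11.9% |
| 0.3 | 20.9% | 10.5% |
| 0.5 | 18.2% | 9.1% |
| 0.7 | 14.8% | 7.4% |
| 0.9 | 10.2% | 5.1% |

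With AST and ALT correlated at 0.8 and all other pairs at 0.2, the figures are 20.4% and 10.3%.

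The reference values for a single test are 5% and 2.5%. Under independence the inflation is 22.6/5 = 4.5-fold for any result and 11.9/2.5 = 4.8-fold for benefit. At correlation 0.9 it is about twofold for both (10.2/5 and 5.1/2.5).

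**Step 4. Would the multivariate test help if it had to succeed first?** The plan does not say that it must. Suppose it did, using a 5-degree-of-freedom chi-square test at 0.05 on independent markers, followed by each marker at 0.05.
- All five null: 4.9% for any false result and 2.9% for a false benefit.
- One marker truly changed (assumed shift of 4 standard errors): about 18% chance of a false result among the other four. This is close to 1 − 0.95^4 = 0.185, because the real effect nearly always carries the overall test.

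Such a first step would protect only the case in which nothing changes.

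**Step 5. Cost of adjusting.** Holm's procedure compares the smallest of five p-values with 0.05/5 = 0.01. Using 0.01 for all five independent markers gives 1 − 0.99^5 = 0.049 for any false result and 1 − 0.995^5 = 0.025 for benefit. A marker with 80% power at 0.05 has an expected test statistic of 1.960 + 0.842 = 2.802. At 0.01 the critical value is 2.576, so power is Φ(2.802 − 2.576) = Φ(0.226), about 59%.

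**The case against.** The strongest reply is that this is ordinary practice. The plan names one primary endpoint and keeps it apart from the secondaries. Small single-clinic studies often leave secondary tests unadjusted. The plan also recognises the multiple measures, and its word for the multivariate work leans towards exploration. Chi-square or analysis of covariance could identify the marker that the overall test cannot.

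Part of this stands. Unadjusted secondary tests do not raise the error rate of the primary comparison, and a reader should not infer that they do. Adding the primary to the family to reach 1 − 0.95^6 = 26.5% has no basis in the document. The plan also does not say outright that each secondary will be tested and claimed separately, so the percentages are conditional on that.

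The reply does not remove the point. Only the multivariate analysis is described as exploring; the secondary endpoints are not. The significance rule expressly covers the whole study. The availability of tests for single markers is what opens the route to an unadjusted claim, and nothing says how those tests and the overall test work together.

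**Conclusion.** The point holds in a limited form. Under the stated rule, if the five markers are tested separately and none changes, the chance of at least one false significant result is about 23% under independence, with a bound of 25%. The chance of a false benefit is about 12%, with a bound of 12.5%. Assumed correlations of 0.3 to 0.9 lower these to about 21% to 10%, and about 10% to 5%. The multivariate analysis as written does not control single-marker claims.

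Three stronger readings are tempting and are not supported:
- **That 23% is the chance of a false benefit.** The rule is two-sided, so 23% includes apparent harm. The figure for benefit is about half.
- **That 23% is a ceiling.** It is the value under independence.
- **That the inflation is at least threefold whatever the correlation.** At 0.7 the chance of any false result is 14.8%, just under three times 5%. At 0.9 it is 10.2%, about twice.

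This concerns what may be claimed from the secondary endpoints. It is no defect in the primary test.

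**What to change.** Amend Data Analysis, B. Statistical Methodology, along these lines:

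- The two-sided 0.05 significance criterion applies only to the single primary comparison of fibrosis between arms.
- AST, ALT, HbA1c, BMI and LDL are each reported as a baseline-adjusted between-arm difference with a 95% confidence interval. They are labelled exploratory, and the intervals are not adjusted for multiplicity.
- The multivariate analysis is named and serves as descriptive support. It does not license a claim about a single marker.

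This takes two or three sentences, with no added subjects, visits or tests. The downside is that no individual secondary marker can be claimed as statistically significant.

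If the sponsor wants such claims, Holm's procedure across the five can be stated in advance, with the smallest p-value compared with 0.01. That is a real trade-off: a marker with 80% power at 0.05 has about 59% at the 0.01 step. Requiring the multivariate test to succeed first is not an adequate substitute, for the reason in step 4 of the working.
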